Patients in Part A, Period 2 will stay on their assigned dose for a maximum of 24 weeks or until they meet the criteria for loss of regrowth maintenance (LOM), defined as an absolute SALT score >20. Any patient meeting the LOM criteria at any assessment timepoint during Part A, Period 2 will enter Part B of the study and return to their original CTP-543 treatment from Part A, Period 1 (8 mg BID or 12 mg BID). Patients not meeting the LOM criteria (e.g., their absolute SALT score remains \leq 20) at the end of 24 weeks will have the opportunity to continue receiving treatment in the Open-Label Extension study (CP543.5001) or they will complete treatment at Week 24 and return in 4 weeks for the Post-Treatment Safety Follow-up.

Assessment of treatment response using SALT for efficacy will occur at 4, 8, 12, 16, 20 and 24 weeks. The primary efficacy analysis will be conducted when all patients have completed Week 24 of Part A, Period 2. The study design is depicted below.

Part A: Treatment and Dose Modification Phase

Part B: Re-Treatment Phase

Part B: Re-

Figure 2: CP543.2004 Study Design

LOM: Loss of Maintenance

Part B (Re-Treatment Phase)

Any patient from Part A, Period 2 meeting the LOM criteria (SALT > 20) will enter into Part B of the study and return to their original 8 mg BID or 12 mg BID dose assigned in Part A, Period 1. Patients will stay on their assigned dose for 24 weeks regardless of whether they meet the criteria for Restoration of Regrowth (ROR) or not. ROR is defined as the patient's attainment of an absolute SALT score ≤20. Assessment of treatment response using SALT for efficacy will occur monthly during the 24-week period. Patients will have the opportunity to continue receiving treatment in the Open-Label Extension study (CP543.5001) or they will complete treatment at Week 24 and return in 4 weeks for the Post-Treatment Safety Follow-up.

Safety

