receiving the 12 mg BID) or placebo. Patients in Part A, Period 2 will stay on their assigned dose for a maximum of 24 weeks or until they meet the criteria for loss of regrowth maintenance (LOM), defined as an absolute SALT score  $>20$ . Any patient meeting the LOM criteria at any assessment timepoint during Part A, Period 2 will enter Part B of the study and return to their original CTP-543 treatment from Part A, Period 1 (8 mg BID or 12 mg BID). Patients not meeting the LOM criteria (e.g., their absolute SALT score  $\leq 20$ ) at the end of 24 weeks will have the opportunity to continue receiving treatment in the Open-Label Extension study (CP543.5001) or they will complete treatment at Week 24 and return in 4 weeks for the Post-Treatment Safety Follow-up. The study design is depicted in the Study Flow Chart of the Appendix (Section 15.1).

An interim analysis to support regulatory activities related to an upcoming CTP-543 New Drug Application (NDA) submission will be conducted. The focus of the interim analyses will be on safety data and will occur following completion of Part A, Period 1. Additionally, after Part A, Period 1 completion, a PK population analysis will be completed. The PK analysis will be conducted by an outside vendor. This analysis will be described in a separate analysis plan and a separate report will be generated.

The primary efficacy assessment will be conducted when all patients have completed Part A, Period 2. An analysis of safety data will also be conducted. This analysis will be included in the NDA submission as an abbreviated report. Site personnel and patients will remain blinded to individual patient study treatments.

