The following disposition information will be summarized for Part A Period 2:

- The number of patients randomized.
- The number and percentage of randomized patients within the Efficacy and Safety Populations.
- The number and percentage of randomized patients who:
  - completed treatment in Part A Period 2 per the *Treatment Discontinuation/Completion* eCRF page, where completed includes the following subcategories: complete-LOM achieved-entering Part B, complete-entering Open Label, and complete-safety follow-up.
  - prematurely discontinued treatment in Part A Period 2.
    - The frequency and percentage of each discontinuation reason. The denominator for the percentage of each discontinuation reason will be the number of patients who discontinued treatment in Part A Period 2.
  - prematurely discontinued treatment in Part A Period 2 due to COVID-19
    - The frequency and percentage of reasons related to COVID-19. The denominator for the percentage of reasons related to COVID-19 will be the number of patients who discontinued treatment due to COVID-19.
  - completed the study in Part A Period 2 per the *Study Discontinuation/Completion* eCRF page, where completed includes the following subcategories: complete-LOM achieved-entering Part B, complete-entering Open Label, and complete-safety follow-up.
  - prematurely discontinued the study in Part A Period 2.
    - The frequency and percentage of each study discontinuation reason. The denominator for the percentage of each discontinuation reason will be the number of patients who discontinued the study in Part A Period 2.
  - prematurely discontinued the study due to COVID-19
    - the frequency and percentage of reasons related to COVID-19. The denominator for the percentage of reasons related to COVID-19 will be the number of patients who discontinued treatment due to COVID-19.

The following disposition information will be summarized for Part B:

- The number of patients re-randomized.
- The number and percentage of re-randomized patients within the Efficacy and Safety Populations.

Concert Pharmaceuticals, Inc.  
Statistical Analysis Plan – CP543.2004

- The number and percentage of re-randomized patients who:
  - completed treatment in Part B per the *Treatment Discontinuation/Completion* eCRF page, where completed includes the following subcategories: complete-entering Open Label and complete-safety follow-up.
  - prematurely discontinued treatment in Part B.

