    - The frequency and percentage of each discontinuation reason. The denominator for the percentage of each discontinuation reason will be the number of patients who discontinued treatment in Part B.
  - prematurely discontinued treatment in Part B due to COVID-19
    - The frequency and percentage of reasons related to COVID-19. The denominator for the percentage of reasons related to COVID-19 will be the number of patients who discontinued treatment due to COVID-19.
  - completed the study in Part B per the *Study Discontinuation/Completion* eCRF page, where completed includes the following subcategories: complete-entering Open Label and complete-safety follow-up.
  - prematurely discontinued the study in Part B.
    - The frequency and percentage of each study discontinuation reason. The denominator for the percentage of each discontinuation reason will be the number of patients who discontinued the study in Part B.
  - prematurely discontinued the study due to COVID-19
    - the frequency and percentage of reasons related to COVID-19. The denominator for the percentage of reasons related to COVID-19 will be the number of patients who discontinued treatment due to COVID-19.

The number and percentage of patients randomized within each treatment group will also be summarized by investigative site for each Part and Period of the study.

Disposition and patient visits will also be presented for each patient in patient data listings. Patient data listings will list date of informed consent, date of first/last treatment, date of end of treatment/early treatment termination, date of end of study/early study termination, and reasons for treatment or study discontinuation. A Kaplan Meier curve of time to early treatment termination for any reason by study part will also be presented for the Safety Population. Patients who have completed treatment will be censored at date of last treatment or a maximum of 24 weeks. Consort diagrams may also be presented.

Screen failures will be provided in a separate listing. Rescreened patients who later enrolled will not be listed as screen failures.

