Table	14.3.5.1.1	Vital Signs Summary — Part A Period 1	Safety Population	
Table	14.3.5.1.2	Vital Signs Summary — Part A Period 2	Safety Population	
Table	14.3.5.1.3	Vital Signs Summary — Part B	Safety Population	
Table	14.3.5.2.1	Presence or Absence of Nasal Hair by Treatment Group and Visit — Part A Period 1	Safety Population	Y
Table	14.3.5.2.2	Presence or Absence of Nasal Hair by Treatment Group and Visit — Part A Period 2	Safety Population	Y
Table	14.3.5.2.3	Presence or Absence of Nasal Hair by Treatment Group and Visit — Part B	Safety Population	
Table	14.3.5.3.1	12-Lead Electrocardiogram Summary — Part A Period 1	Safety Population	
Table	14.3.5.3.2	12-Lead Electrocardiogram Summary — Part A Period 2	Safety Population	
Table	14.3.5.3.3	12-Lead Electrocardiogram Summary — Part B	Safety Population	
Table	14.3.5.4.1	Summary of Missing or Remote Visits Related to COVID-19 by Treatment Group — Part A Period 1	Safety Population	
Table	14.3.5.4.2	Summary of Missing or Remote Visits Related to COVID-19 by Treatment Group — Part A Period 2	Safety Population	

Concert Pharmaceuticals, Inc.  
Statistical Analysis Plan – CP543.2004

Type	Number	Title	Population	For abbreviated report?
Table	14.3.5.4.3	Summary of Missing or Remote Visits Related to COVID-19 by Treatment Group — Part B	Safety Population	
Figure	14.1.1.1	Summary of Patient Disposition — CONSORT Diagram — Part A Overall	All Screened Patients	Y
Figure	14.1.1.2	Summary of Patient Disposition — CONSORT Diagram — Part A and Part B	All Screened Patients	
Figure	14.1.2.1	Kaplan-Meier Plot for Time to Treatment Discontinuation — Part A Period 1	Safety Population	Y
Figure	14.1.2.2	Kaplan-Meier Plot for Time to Treatment Discontinuation — Part A Period 2	Safety Population	Y
Figure	14.1.2.3	Kaplan-Meier Plot for Time to Treatment Discontinuation — Part B	Safety Population	
Figure	14.2.1.1	Patients Achieving Loss of Regrowth Maintenance (SALT Score $>20$ ) or Response (SALT Score $\leq 20$ ) by Treatment at End of Part A Period 2 — Part A Period 2	Efficacy Population	Y
Figure	14.2.2.1.1	Responders (SALT Score $\leq 20$ ) by Treatment across Time — Part A Period 1	Efficacy Population	Y
Figure	14.2.2.1.2	Loss of Regrowth Maintenance (SALT Score $>20$ ) by Treatment across Time — Part A Period 2	Efficacy Population	Y
Figure	14.2.2.1.3	Responders (SALT Score $\leq 20$ ) by Treatment across Time — Part A Period 2	Efficacy Population	Y

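### The Period 2 Kaplan-Meier curve of early treatment termination censors LOM exits, so its complement can exceed the share of patients who actually stop early

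*SAP*

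**What the plan says.** SAP 6.1 (Disposition of Subjects) states: "A Kaplan Meier curve of time to early treatment termination for any reason by study part will also be presented for the Safety Population". Its censoring rule is "Patients who have completed treatment will be censored at date of last treatment or a maximum of 24 weeks".

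The same section defines treatment completion in Period 2 to include "complete-LOM achieved-entering Part B, complete-entering Open Label, and complete-safety follow-up". A LOM exit is therefore a completion, and the rule censors it at the last Period 2 treatment date.

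Protocol 8.1 makes the exit mandatory: "Any patient meeting the LOM criteria at any assessment timepoint during Part A, Period 2 will enter Part B of the study". LOM can be found at any Period 2 SALT visit, and Protocol 8.1 schedules these as follows: "Assessment of treatment response using SALT for efficacy will occur at 4, 8, 12, 16, 20 and 24 weeks".

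SAP 15.4 lists the display as Figure 14.1.2.2, "Kaplan-Meier Plot for Time to Treatment Discontinuation — Part A Period 2", and marks it for the abbreviated report. The SAP names no competing-risk method. Table 14.1.1.2, also marked for that report, gives premature Period 2 treatment discontinuation as a count and a percentage of randomised patients.

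**The concern.** A patient who leaves for Part B at Week 8 of Period 2 can no longer terminate Period 2 treatment early. Kaplan-Meier removes that patient from the risk set and implicitly gives them the later termination risk of those who remain. That suits a patient whose follow-up is merely cut short. Here the event has become impossible, and the protocol itself makes it so.

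A disposition curve invites the reader to take its drop as the share of patients who stopped. In Period 2 that reading can be too high. The last part of the curve can also rest on very few patients, because LOM exits empty the risk set. The abbreviated report would then hold a curve and a disposition table that appear to disagree, with nothing in the SAP to explain why.

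The issue is specific to Period 2. In Period 1 and Part B treatment is planned for a fixed 24 weeks, so completers are censored near the end of the time axis.

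**Working it through.** The plan states no figure for this curve, so there is nothing to reproduce. The check compares 1-KM under the SAP rule with the Aalen-Johansen cumulative incidence, treating LOM exit as competing.

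**Inputs from the documents.** About 25 patients per Period 2 arm (about 50 Responders per dose group, randomised 1:1: 50/2 = 25; SAP 7.2). LOM visits at Weeks 4, 8, 12, 16, 20 and 24 (Protocol 8.1). LOM exits are completers and are censored (SAP 6.1).

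**Inputs assumed.** The documents give neither LOM nor dropout rates. Net LOM by Week 24 is varied from 0 to 90%, and net dropout from 5 to 30%. Net means the rate if the other event did not occur.

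**1. Worked arm of 25.** Early terminations at Weeks 6, 14 and 22. LOM exits: 4 at Week 8, 6 at Week 12, 4 at Week 16 and 3 at Week 20, 17 in all.

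- At risk at Week 6: 25. At Week 14: 25 - 1 - 10 = 14. At Week 22: 14 - 1 - 7 = 6.
- 1-KM = 1 - (24/25)(13/14)(5/6) = 25.7%.
- Aalen-Johansen = 1/25 + (14/25)(1/14) + (6/25)(1/6) = 3/25 = 12.0%, the crude share.

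The same three terminations with other LOM patterns:

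| LOM exits | 1-KM | Cumulative incidence |
|---|---|---|
| 0 | 1 - (24/25)(23/24)(22/23) = 12.0% | 12.0% |
| 4 (one at Week 12, one at Week 16, two at Week 20) | 1 - (24/25)(22/23)(18/19) = 13.0% | 12.0% |
| 17 (as above) | 25.7% | 12.0% |

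If the three terminations instead fall before the first LOM exit, both methods give 12.0%.

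**2. Large-sample calculation.** There are six 4-week intervals. With net dropout d and net LOM L, the interval hazards are h = 1 - (1-d)^(1/6) and l = 1 - (1-L)^(1/6), and q = (1-h)(1-l). Then 1-KM = d, and cumulative incidence = h(1 - q^6)/(1 - q).

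For d = 10% and L = 80%: h = 0.0174, l = 0.2353, q = 0.7514 and q^6 = 0.9 × 0.2 = 0.18. Cumulative incidence = 0.0174 × 0.82/0.2486 = 5.7%, against 1-KM of 10.0%.

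| Net dropout | Net LOM | 1-KM | Cumulative incidence | Gap (points) | Ratio |
|---|---|---|---|---|---|
| 10% | 20% | 10.0% | 9.1% | 0.9 | 1.09 |
| 10% | 60% | 10.0% | 7.1% | 2.9 | 1.41 |
| 10% | 80% | 10.0% | 5.7% | 4.3 | 1.74 |
| 10% | 90% | 10.0% | 4.8% | 5.2 | 2.09 |
| 20% | 80% | 20.0% | 11.7% | 8.3 | 1.72 |
| 5% | 80% | 5.0% | 2.9% | 2.1 | 1.75 |
| 30% | 20% | 30.0% | 27.6% | 2.4 | 1.09 |

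**3. Simulated arms of 25** (4,000 per scenario). The mean gap is 0.9 points at 10% dropout and 20% LOM, 4.5 points at 10% and 80%, and 8.0 points at 20% and 80%. It was never negative. At 10% dropout and 80% LOM, the standard deviation of the Week 24 value is about 9.2 points for 1-KM and 4.7 points for the incidence.

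**The case against.** The strongest defence is that Kaplan-Meier with LOM censored is a legitimate curve of the tendency to stop while still on Period 2 treatment, provided LOM exit is unrelated to the risk of stopping. The error lies only in reading its complement as a proportion of patients. SAP 6.1 does not present it that way, and SAP 15.4 lists no table of Kaplan-Meier estimates for treatment discontinuation. The crude percentages are already in Table 14.1.1.2, and the study is descriptive. All this stands, and it limits the weight of the point. It does not remove it. No label tells the reader that the curve is conditional on remaining in Period 2. Since LOM always ends Period 2 treatment, 1-KM also describes a setting that the design does not allow.

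A reader might go further and infer that the planned curve would make the drug-discontinuation arms look worse tolerated or worse retained than they are. That does not follow. With equal dropout hazards, 1-KM is the same in every arm: 10.0% at both 20% and 80% LOM in the table. It is the cumulative incidence that then differs, 9.1% against 5.7%, because patients leave for Part B before they can stop.

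Nor need the gap always be largest where LOM is highest. With 30% dropout and 20% LOM it is 2.4 points, against 2.1 points with 5% dropout and 80% LOM.

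Finally, curves split by arm are an inference from the by-treatment convention in SAP 4. Neither SAP 6.1 nor the figure title says so.

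**Conclusion.** The point holds as a matter of method and is modest in consequence. Taken together, the completion categories and the censoring rule in SAP 6.1 treat a competing event built into the design as ordinary censoring. The direction is certain: 1-KM is never below the share who stop early, and it exceeds that share once a termination follows a LOM exit.

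The size cannot be taken from the documents. For a given dropout hazard the overstatement grows with the LOM rate. Over assumed dropout of 5 to 30%, it is about 1.09-fold at 20% LOM, 1.7-fold at 80%, and 2.0- to 2.1-fold (at most 15 points) at 90%. These figures rest on constant hazards. At 10% dropout and 80% LOM with 25 patients, the average gap is about half a standard deviation of the plotted value, so instability matters as much as bias. The 25.7% against 12.0% example is constructed to show the mechanism and is not a forecast.

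No primary or secondary endpoint changes, and Table 14.1.1.2 remains correct.

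**What to change.** In SAP 6.1 and Figure 14.1.2.2, replace the Period 2 Kaplan-Meier curve with Aalen-Johansen cumulative incidence curves. Make early treatment termination the event and LOM exit to Part B the competing event. Show both on one figure with numbers at risk, and state whether they are drawn by arm. Censor only patients who reach 24 weeks without either event, or who are ongoing at a data cut. Keep Kaplan-Meier for Period 1 and Part B.

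SAP 8.1.3 places the abbreviated-report analyses after the last patient completes Part A, so no Period 2 patient should then be ongoing. The Week 24 value will then match the crude percentage in Table 14.1.1.2, apart from any randomised patient outside the Safety Population or analysed under a different treatment.

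The cost is a small change to the SAP text and one figure program, with no new data. The drawback is that cumulative incidence is lower in high-LOM arms simply because patients leave for Part B, so it must not be read as a comparison of on-treatment tolerability. If a Kaplan-Meier curve is also kept for that purpose, label it *LOM exits censored; conditional on remaining in Period 2* and show numbers at risk.

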## 6.2. Demographic and Other Baseline Characteristics

Demographic characteristics (i.e., sex, ethnic origin, race, age, and calculated body mass index) will be collected at the Screening Visit, between Day -28 and -1, and detailed on the eCRF.

Demographic characteristics will be summarized using descriptive statistics for all randomized patients by treatment group and overall, for each of Part A Period 1, Part A Period 2, and Part B.

Concert Pharmaceuticals, Inc.  
Statistical Analysis Plan – CP543.2004

Baseline characteristics will be summarized using descriptive statistics for all randomized patients by treatment group and overall, for each study part, and will include the following:

- Baseline total SALT score
  - Note: Baseline total SALT score for Part A Period 2 will be the last SALT score obtained prior to dosing in Part A, Period 2 (ie, Week 24 SALT assessment from Part A, Period 1). Part B baseline total SALT score will be the last SALT score obtained in Part A, Period 2 prior to re-randomization into Part B.
- Alopecia areata classification (randomization strata): partial scalp hair loss (SALT  $\geq$  50 and < 95); complete or near-complete scalp hair loss (SALT  $\geq$  95)
- duration of current episode in years (calculated as: [date of randomization – date of current episode onset + 1] / 365.25)
- nasal hair involvement

For Part A Period 1, whether the patient has experienced any past and/or concomitant diseases, conditions, or exposures to serious infections (such as HIV), or past surgeries will also be summarized with baseline characteristics.

Other co-morbidities may be identified and included as baseline characteristics.

All demographics and baseline characteristics will also be listed within a by-patient data listing for all randomized patients.

### **6.3. Prior and Concomitant Medications**

Concomitant medications will be recorded in the eCRF from Screening through the Follow-Up Visit at Week 28, for all Parts/Periods of the study. All medications will be coded using the WHO Drug Dictionary Version 2020-SEP.

Medications are classified as prior if the medication started prior to the first dose date of study drug or as concomitant if used on or after the first dose date of study drug for a given Part/Period.

Prior and concomitant medications will be summarized with counts and percentages separately for the Safety Population by treatment group, WHO Drug ATC classification level 2 and preferred term. For each summary, a patient will be counted only once for each medication.

Prior medications will be summarized for Part A Period 1 only. Concomitant medications will be summarized for each Part/Period.

Partial and completely missing dates will be imputed for the purposes of classifying concomitant medications as follows:

- Partial dates will be imputed following the same algorithm as in Section 9.3 for Treatment-emergent adverse events (TEAEs).
- For an entirely missing start date (i.e. day, month, and year are missing), the start date will be set to the date of administration of study drug for the given Part/Period unless the

Concert Pharmaceuticals, Inc.  
Statistical Analysis Plan – CP543.2004

stop date is prior to the date of administration of study drug, in which case the start date will be set to the stop date.

- For an entirely missing stop date (i.e. day, month, and year are missing), the medication will be treated as ongoing.

Partial dates will be compared to the start and end dates of each Part/Period to determine the study drug administration date that will be used to be imputed.

Prior and concomitant medications will also be listed by-patient.

